Unfortunately, there is still very little experience with this type of study in multifactorial diseases such as thyrotoxicosis. Given that the study examines an extremely selected phenotype (due to inclusion and exclusion criteria), and the standard deviation (variance) cannot be predicted with certainty, the strength calculation is expected to be subject to uncertainty. Assuming that the standard deviation is 10, alpha is 0.05, cases 80 and controls 200, there will be 80% power to detect a genetic variant with an Odds Ratio of 5 between cases and controls. This is considered to be a clinically relevant difference between the two groups.

Methods

Participants and recruitment

Participants are recruited from the Endocrinology Outpatient Clinic at Rigshospitalet and Herlev/Gentofte Hospital. A list of the departments' patients with a diagnosis of thyrotoxicosis (ICD 10 E05) is extracted. By screening medical records and ICD10 codes it will be possible to select potential participants with Graves' disease. However, there is a risk that some patients are not identified by the above mentioned extraction due to incorrectly registered ICD 10 codes. Therefore, an extraction will be made from the Department of Clinical Biochemistry of all patients in the relevant age group with positive "Thyrotropin Receptor Antibody (TRAb) since 01.01.2014. Hereby, identifying as many patients with Graves' disease as possible. The latter screening method can be initiated once the ethical approval has been obtained.

Patients meeting the following inclusion and exclusion criteria will then be sent a questionnaire with questions about whether the person has persisting cardiac symptoms (Appendix 1). Following the recommendation of the Research Ethics Committee, it is decided to also enclose a copy of the participant information. The potential trial participant is made aware that if they are interested in participating after reading the participant information, they must send a completed questionnaire back to us. Once the questionnaires have been returned, patients with persistent cardiac symptoms will be contacted either by telephone or by letter in the e-health platform.

Inclusion criteria

Patients with Graves' disease between the ages of 18 and 55 years at study entry who #) have been euthyroid for at least three months prior to inclusion and ##) experience one or more cardiac symptoms.

#) Blood tests are used to assess euthyroidism:

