3. Transthoracic echocardiography (ultrasound of the heart). The examination provides anatomical information about the pericardium, myocardium, ventricles, heart valves and central vessels, as well as quantitative information about the myocardium's pumping ability, haemodynamics and valve function. The recordings are blinded and analyzed by supervising echocardiographer and consultant [name].
4. The exercise stress test is performed as a physical load test on an ergometer bike with standardized increase (25W at start, 25W increase every 2 minutes) of the workload while simultaneously monitoring symptoms, blood pressure and 12-lead

ECG before, during and after the test. The investigation shall be conducted in accordance with the protocol available on Cardio.dk. The purpose of the study is to assess the development of arrhythmias, the functioning of the autonomic nervous system and work capacity. The maximum heart rate and time to this, resting heart rate, and time from max heart rate to resting heart rate are measured.

Genetic analyses

3 x 9 ml of blood is drawn for genetic analyses. The blood is transferred to EDTA glass and glass with Trasylol and frozen and stored at -80 degrees. Purification of DNA is performed at the Laboratory of Molecular Cardiology, Rigshospitalet Heart Center, using the Maxwell 16 LEV blood DNA Kit (sold by Promega; Wisconsin, USA). Later, genotyping is carried out using ChIP technology at the *Institut für Klinische Molekularbiologie, Universitätsklinikum*, Schleswig-Holstein, Kiel, Germany. This is not a whole-genome sequencing study. The study aims to investigate single nucleotide polymorphisms (SNP) in specific regions of the genome. The study uses SNP-array/SNP genotyping, where the analysis is based on general genetic variation and not mapping of the genome. The results are used to map risk loci and to determine plausible disease-causing genes. The study will give an understanding of the most common variants in Graves' patients, and with the possibility of comparing these with the Næstved cohort and the United Kingdom Biobank (UKBB) as well as being able to compare the variants with control groups. The aim of the study is to determine the significance of the sum of genetic variants' for the development of disease, called the Polygenic Risk Score.

Excess biological material is sent back to Denmark when the analyses in Germany have been carried out. The material is then stored in a biobank, see page 10.

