Analyses of participants are compared with analyses of Graves' patients from the Næstved cohort

- The trial participants with Graves' disease will undergo genotyping and the results of this will be compared with findings of variants determined in 20,000 of a general population of 70,000 individuals (the Næstved cohort which has been followed over 20 years) in which the incidence of Graves' disease is about 25 out of 100,000 per year (The project is approved in VEK SJ-114). The Næstved cohort is an already genotyped (SNP-genotyped, not whole-genome) cohort of patients. Members of our research group are the managers of the Næstved project. Therefore, it is in our

interests to compare genetic variants found in Graves' patients with a control cohort that we already know and have previously genotyped. Consent is not obtained from the participants of the Næstved cohort because no new studies of the participants' genome are carried out. Thus, there are no health consequences for the Næstved cohort's patients' participation in this project, nor elements of a research perspective that the patients must consider.

- Variants found are further verified using data from the UKBB on about 500,000 individuals. The UKBB contains clinical and genetic data on 457 patients with Graves' disease. There is no question of importing biological material from these patients. Through a data agreement with UKBB, our research group has access to anonymised patient information on British individuals. This includes SNP genotyping, MRI scans, ECGs, etc. Hereby, the data agreement enables us to compare our results with similar patients.

Biobank

Blood samples will be pseudoanonymized and stored for later supplementary genetic, biochemical, histological, and other pathoanatomical studies. Thus, a research biobank will be established in connection with the project. At the end of the project, the biological material will be stored in a fully anonymized manner at the Laboratory of Molecular Cardiology in a conventional biobank. The biological material will be stored for 20 years and will only be included in further research projects with the consent of the participants or with an exemption from the consent given by the research ethics committee. The data protection rules are complied with when any type of biological material is stored in our biobank.

Study design

Visit 1: Informative visit, anamnesis, and paraclinical examinations

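### The 80% power figure is for one variant at an unadjusted alpha of 0.05; it describes neither the planned multi-variant locus mapping nor the polygenic risk score aim

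*Protocol*

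**What the plan says.** All places are in the Protocol.

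- **Genetic analyses and statistical considerations** gives the inputs ("Assuming that the standard deviation is 10, alpha is 0.05, cases 80 and controls 200") and concludes that "there will be 80% power to detect a genetic variant with an Odds Ratio of 5 between cases and controls". No other error rate or power figure appears. No variant frequency, number of variants or sidedness is given.
- **Genetic analyses** (under Examination methods) limits the scope: "The study aims to investigate single nucleotide polymorphisms (SNP) in specific regions of the genome". It describes the platform: "The study uses SNP-array/SNP genotyping, where the analysis is based on general genetic variation and not mapping of the genome". It then states the use: "The results are used to map risk loci and to determine plausible disease-causing genes". The same section names the PRS, the sum of variants, as the aim.
- **Analyses of participants are compared with analyses of Graves' patients from the Næstved cohort** adds a second step, "Variants found are further verified using data from the UKBB on about 500,000 individuals", without saying what counts as verified. It also names a comparison set of 20,000 genotyped individuals.

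**The concern.** An alpha of 0.05 for a single variant suits one variant named in advance. Mapping loci from an array involves one comparison per variant, even when the work is confined to chosen regions. The level used to justify 80 cases is therefore not a level at which a locus search is normally judged, and the protocol does not link the two.

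Two things are at stake. If the 0.05 in the power statement is carried over as the per-variant decision level, chance findings can be reported as risk loci or plausible genes. If a stricter level is used, the 80% was worked out at a different level and must be shown again. The PRS, which is the named aim, has no power statement at all.

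**Working it through.** **Inputs from the protocol:** 80 cases, 200 controls, odds ratio 5, alpha 0.05, power 80%. **Assumed, because not given:** two-sided tests, the variant frequency in controls (p0) and the number of independent variants (m).

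**1. Reproducing the 80%.** With p1 = 5·p0 / (1 + 4·p0), power = Φ[(p1 − p0 − z·SE0) / SE1]. SE0 is the standard error from the pooled proportion and SE1 the one from the separate proportions. The carrier model has 80 v 200 people; the allelic model has 160 v 400 alleles.

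Solving for 80% gives p0 ≈ 2.5% carriers or ≈ 1.2% allele frequency, plus a mirror solution at very high frequency (86% carriers, 93% allele frequency). So the figure holds only at a frequency that the protocol does not state. The standard deviation of 10 does not enter an odds-ratio test. Reading the 5 as a mean difference gives 5 / [10·√(1/200 + 1/80)] = 3.78, hence power Φ(3.78 − 1.96) = 96.6%, not 80%.

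**2. The same variant at adjusted levels.** Carrier model, p0 = 0.025: p1 = 0.125/1.1 = 0.1136, difference 0.0886, SE0 = 0.0289, SE1 = 0.0372.

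| Level | z | Power |
|---|---|---|
| 0.05 | 1.960 | 80.5% |
| 0.05/10 | 2.807 | 58.0% |
| 0.05/100 | 3.481 | 37.3% |

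**3. Common variants.** Allelic model at 5e-8 (z = 5.451). For p0 = 0.1: p1 = 0.5/1.4 = 0.357, SE0 = 0.0354, SE1 = 0.0407, so power = Φ[(0.2571 − 5.451·0.0354)/0.0407] = 94%. At p0 = 0.2 and 0.3 it is 99.7% and 99.9%. At 0.05 it is 60% and at 0.02 it is 12%.

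The carrier model is less favourable. With 10% carriers, power is 92% at 0.05/100, 69% at 0.05/10,000 and 39% at 5e-8.

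**4. False hits if 0.05 were used per variant.** With independent null variants, P(at least one) = 1 − 0.95^m and the expected number is 0.05·m. If UK Biobank verification required two-sided p < 0.05 in the same direction (an assumption), the expected number left is 0.05 × 0.025 × m.

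| m | P(at least one) | Expected | Left after verification |
|---|---|---|---|
| 14 | 51% | 0.7 | 0.02 |
| 59 | 95% | 3 | 0.07 |
| 100 | 99.4% | 5 | 0.1 |
| 1,000 | ~100% | 50 | 1.3 |
| 10,000 | ~100% | 500 | 12.5 |

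**The case against.** The other side has several good points.

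- **0.05 is only a power input.** No section makes it the level for calling a locus, and that rule may sit in a statistical analysis plan that is not shown. This stands. A reader might infer that false loci are near certain or that false positives are uncontrolled; the protocol does not say so.
- **Findings are verified in UK Biobank.** Under the assumed criterion this is adequate for a short regional list (0.1 false loci expected per 100 variants) but not for a wide scan (about 12 per 10,000). Neither the list length nor the criterion is stated.
- **Only specific regions are studied.** A genome-wide level may be harsher than needed. But 14 independent variants are enough to make a false hit more likely than not at 0.05.
- **The variants are common.** The Risk/benefit assessment says that frequent variants are studied, and for these an odds ratio of 5 can keep 80% power at a strict level. This stands for the allelic model, and it means that the power loss cannot be separated from the missing frequency.
- **More controls may be available.** If all 20,000 genotyped individuals served as controls, allelic power at 5e-8 and frequency 0.05 would rise from 60% to about 98%. The power statement nevertheless uses 200.
- **The PRS can be tested as one score.** Per-variant correction does not then apply to it. This stands, but the single-variant figure is not a power figure for that test.

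The protocol also admits that its power calculation is uncertain. It attributes this to the selected phenotype and the unpredictable standard deviation, not to the number of tests.

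**Conclusion.** The point holds in a limited form. The protocol does not merely leave multiplicity to a later document: it fixes alpha at 0.05 and rests 80% power for 80 cases on it. That figure is for one unadjusted single-variant test and does not describe the locus mapping or the PRS aim.

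The size depends on frequency and on the number of variants. Near 2.5% carriers, where the protocol's own 80% is met, power falls to 58% for 10 variants and 37% for 100. For allele frequencies of 0.1 to 0.3 in the allelic model, the claim survives even at 5e-8. These results assume two-sided normal-approximation tests, independent variants and Bonferroni levels.

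Two stronger conclusions are not supported. One is that either the alpha or the power must be wrong: for common variants a strict level and 80% power for an odds ratio of 5 can both hold. The other is that the power figure is for a test that the study will not do: variant-by-variant comparisons with controls are planned, and it is the level and the number of tests that do not match.

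**What to change.** 1. In Genetic analyses and statistical considerations, replace alpha 0.05 by the per-variant level: 0.05 divided by the number of independent variants in the chosen regions, or 5e-8 if the whole array is scanned. State that number.
2. In the same place, restate the power or the detectable odds ratio at that level, with the assumed variant frequency and genetic model.
3. In Genetic analyses, use the same level to call a locus.
4. In the Næstved and UK Biobank section, require verification in the same direction at 0.05 divided by the number of variants carried forward.
5. Keep 0.05 for a single pre-specified PRS test, and say that the single-variant power figure does not apply to it.

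This costs protocol wording and one recalculation, with no new participants or procedures. The drawback is that the stated power or detectable odds ratio becomes less favourable for rarer variants. The levels should be fixed before any locus results are seen.

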The study is a collaboration between researchers from the Laboratory of Molecular Cardiology (LMC) Department of Cardiology, Rigshospitalet, Department of Biomedical Sciences, University of Copenhagen, Department of Medical Endocrinology,

Rigshospitalet, and Department of Endocrine Diseases, Department of Medicine, Herlev-Gentofte Hospital.

Purpose

The purpose of the study is to characterize patients who are being treated or have been treated for Graves' disease and have been euthyroid for a minimum of three months, but despite this experience cardiac symptoms.

Patient characteristics include:

- Medical history and symptoms
- Biochemical analyses
- A cardiac workup: resting 12-lead ECG, 24-hour ambulatory electrocardiogram monitoring (Holter analysis), transthoracic echocardiography, and an exercise stress test
- Phenotype/genotype variations

No deviations from standard treatments will be made in the study.

Hypothesis

The hypothesis is that Graves' disease in genetically predisposed individuals will induce cardiac changes that persists months to years after normalization of thyroid hormone concentrations in the blood. This is a previously undescribed condition that could be caused by a remodeling of myocardial tissue and of the autonomic nervous system.

Rationale for the study

Euthyroid patients with a persistent tendency to dyspnoea, intermittent palpitations, and increased heart rate – after treatment of Graves' disease – may have a previously undescribed "syndrome" (cf. textbooks and literature in the reference list (page 19)).

Genetic analyses and statistical considerations

We will use the Polygenic Risk Score (PRS), developed on genetic data from the Næstved Cohort (see page 9) and other cohorts to try to predict who is genetically predisposed to e.g. sinus node and contractile dysfunction. The genetic variants included will be selected

using an algorithm that tries to ensure that each genetic variant is independent. Here, the so-called "pruning and thresholding" method is used [Khera AV 2018].

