- i) Normal S-Thyrotropin [TSH] levels [0,4 – 4,8 x E-3 IU/L]
- ii) Normal total S-Thyroxin [T4] i] levels [70-140 nmol/L]
- iii) Normal free S-Thyroxin [fT4] i] levels [11,5- 22,7 pmol/L]
- iv) S-Triiodothyronine [T3] below the upper reference level [2,6 nmol/L]

The above-mentioned criteria are indicative of euthyroidism. However, several conditions (e.g. presence of other disease) and medications (e.g. other hormones, oral contraceptives, amiodarone, recent scans with iodine contrast) can affect the plasma concentrations. Therefore, the assessment of euthyroidism will ultimately depend on an endocrinological evaluation.

##) Patients who in the questionnaire have indicated that they experience:

- Pounding heartbeats
and/or
- Increased heart rate
and/or
- Irregular heartrate
and/or
- Shortness of breath

Exclusion Criteria

- 1) Cardiovascular disease
- 2) Deemed unsuitable by project staff (e.g. due to language problems)
- 3) Pregnancy
- 4) Alcohol abuse or other abuses

Examination methods

Biochemical analyses

- 60 ml of blood was drawn and transferred to different test tubes with different chemical additives. The blood samples are used for determination of biochemical, hematological and immunochemical parameters in accordance with Rigshospitalet's LabPortal (in casu: S-Hgb, S-Leukocytes, S-ionised Ca²⁺, S-Na, S-K, S-Creatinine, S-ALAT, S-LDH, S-Alkaline phosphatase, S-bilirubin, S-TSH, S-TT3, S-TT4, S-fT4, S-anti-TPO, S-Tg, S-TgAb, S-TRAb, S-TBG, T4-uptake test, S-SHBG, S-proBNP, S-proANP, S-hsCRP, S-CardiolipinAb, P-Renin, Vitamin D).

Paraclinical, cardiac studies

1. Resting 12-lead ECG (standard ECG): 3 bipolar extremity leads (I, II, and III), 3 unipolar extremity leads (aVR, aVL, and aVF), 6 unipolar precordial leads (V1, V2, V3, V4, V5, and V6). Rhythm (sinus and/or ectopic rhythm), cardiac axis, ECG intervals (RR interval, PQ interval, QRS interval), atrial enlargement and ventricular hypertrophy were noted. ECG is analysed after the V-point analysis [MK 18th ed., page 897].
2. 24-hour ambulatory electrocardiogram monitoring with a small portable recorder and subsequent computer analysis with algorithm for narrow QRS complex tachycardia. Examination for cardiac autonomic neuropathy (abnormal heart rate variation). During the ECG monitoring the patients keep a diary registering palpitations, near-/fainting, shortness of breath and chest discomfort.

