The purpose of the visit is to check whether the potential participant meets the criteria for participating in the study and to inform the participant about the study prior to any consent. The potential participant has received a telephone call prior to the visit (see above) where the questionnaire is discussed. Furthermore, the trial participant has received written information on the study (appendices 1 and 2). The informative visit and examinations can be carried out during the same visit, which takes place at the LMC. This is provided that

the participant gives his/her consent immediately after the informative meeting. If the potential participant wishes 24-hour reflection time another meeting will be arranged for blood tests and ECG. The duration of the meeting is approximately 1 hour and includes:

- 1) Oral information, clarification of any questions
- 2) Conversation about informed consent and 24-hour reflection time
- 3) The signature of informed consent is ensured before any examinations
- 4) Questions concerning:
 - Inclusion and exclusion criteria
 - Medical history related to Graves' disease (onset, duration, treatment, family history, associated Graves' orbitopathy, smoking)
 - Medicine
 - Symptoms
 - Other diseases
- 5) Further classification of cardiac symptoms through a questionnaire regarding grading of the symptoms.
- 6) Objective examination including blood pressure, height, and weight
- 7) Blood samples for biochemical and genetic analysis
- 8) 12-lead resting ECG

Visit 2:

The visit takes place at LMC, lasts approximately 1 hour, and includes:

- 1) Echocardiography
- 2) Attachment of ECG electrodes connected to a recorder for 24-hour ambulatory electrocardiogram (Holter)

Visit 3:

The visit takes place at the Cardiology Outpatient Clinic, Section 2003, Rigshospitalet. It lasts approximately 1 hour and includes:

- 1) exercise stress test

Visit 4:

The visit takes place at the Endocrinology Clinic, lasts approximately 1 hour, and includes:

- 1) Information about the results of the cardiac examinations
- 2) Conversation about the possibilities of drug treatment

Visit 5:

The visit takes place at the Endocrinology Clinic, lasts approximately 1/2 hour, and includes:

- 1) Information about the results of the genetic tests
- 2) Follow-up

Study duration

Recruitment of patients will start as soon as ethical approval is obtained from the research ethics committee. The study is expected to be completed within 5 years.

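### The symptom criterion requires no link to the hyperthyroid phase and no listed exclusion removes a non-cardiac cause, so the case group can mix the hypothesised syndrome with unrelated palpitations or breathlessness

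*Protocol*

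**What the plan says.** The Purpose section describes patients treated for Graves' disease who "have been euthyroid for a minimum of three months, but despite this experience cardiac symptoms". The Hypothesis section goes further: in genetically predisposed people, Graves' disease itself brings about cardiac changes that last for months to years after hormone levels normalise.

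Under Inclusion criteria, a participant must "experience one or more cardiac symptoms". Criterion ## puts this into practice as "Patients who in the questionnaire have indicated that they experience" pounding heartbeats, increased heart rate, irregular heart rate or, sufficient on its own, "Shortness of breath".

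The exclusion list begins with "1) Cardiovascular disease". The other entries are pregnancy, alcohol or other abuse, and "Deemed unsuitable by project staff (e.g. due to language problems").

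Participants and recruitment says that the mailed questionnaire contains "questions about whether the person has persisting cardiac symptoms (Appendix 1"), and that respondents with persistent symptoms are then contacted. At Visit 1 staff check eligibility and ask about Graves' history, medicine, symptoms and other diseases. They also carry out "5) Further classification of cardiac symptoms through a questionnaire regarding grading of the symptoms". Haemoglobin is among the blood tests.

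In Genetic analyses and statistical considerations, the protocol describes the phenotype as very tightly selected and credits the eligibility criteria for this.

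**The concern.** The target is a condition caused by Graves' disease, but the entry rule is a present-tense symptom report. Palpitations and breathlessness have many other causes. Under the criterion, a euthyroid Graves' patient with asthma and breathlessness, one with low haemoglobin and a fast pulse, and one whose palpitations long predate the thyroid disease can each enter as a case.

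Two things are at stake.

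- **Cardiac characterisation.** A fast heart rate due to anaemia would look like support for a persistent cardiac effect. A normal work-up in someone breathless from lung disease would look like evidence against it.
- **Genetic comparison.** Cases without the syndrome pull the frequency of any syndrome-specific variant towards that of the controls.

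The protocol describes no comparison group, such as asymptomatic Graves' patients or symptomatic people without Graves' disease, that goes through the same cardiac work-up. Background symptoms therefore cannot be subtracted afterwards. If symptom onset is not recorded, no later analysis plan can recover it.

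**Working it through.** **Step 1. Set the target beside the rule.**

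| Element needed for the hypothesised condition | Where the protocol addresses it | Is it a condition of entry? |
|---|---|---|
| Euthyroid for at least three months | Criterion #, with laboratory ranges and endocrinological evaluation | Yes |
| Symptom present | Criterion ##, one of four by self-report | Yes |
| Symptom persistent | Recruitment text only; not defined | Used for contact; absent from ## |
| Symptom linked in time to the hyperthyroid phase | Not stated. The onset item at Visit 1 belongs to the history of Graves' disease, not to the symptom | No |
| No evident non-cardiac cause | Other diseases asked about and haemoglobin measured; no rule attached | No, except through open-ended staff judgement |

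Persistence, even in its ordinary sense, does not supply the fourth row: palpitations that have been present since before the thyroid disease are also persistent.

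**Step 2. What mixing does to a genetic contrast (illustration).** The protocol states 80% power for an odds ratio of 5 with 80 cases, 200 controls and alpha 0.05. It gives no variant frequency, and its standard deviation of 10 does not enter an odds-ratio test. The 80% can therefore be neither confirmed nor refuted. With a two-sided two-proportion test (normal approximation, pooled variance under the null), it is reproduced exactly at a control carrier frequency p0 of 2.46%:

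- case frequency p1 = 5·p0 / (1 − p0 + 5·p0) = 0.123 / 1.0984 ≈ 0.112
- power = 80%

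Suppose a share f of cases lacks the syndrome and carries the variant at the control frequency. Then:

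- observed case frequency pc = (1 − f)·p1 + f·p0
- observed odds ratio = [pc / (1 − pc)] / [p0 / (1 − p0)]

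For f = 30% and p0 = 2.46%: pc = 0.7 × 0.1119 + 0.3 × 0.0246 = 0.0857. The odds ratio is (0.0857 / 0.9143) / (0.0246 / 0.9754) = 3.72.

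| Assumed f | p0 = 2.46%: OR, power | p0 = 5%: OR, power | p0 = 10%: OR, power |
|---|---|---|---|
| 0 | 5.00, 80% | 5.00, 96% | 5.00, >99% |
| 10% | 4.56, 75% | 4.53, 93% | 4.46, 99% |
| 30% | 3.72, 61% | 3.64, 82% | 3.50, 95% |
| 50% | 2.91, 43% | 2.82, 62% | 2.67, 78% |

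Both f and p0 are assumptions; the documents give neither. Under this model the odds ratio is attenuated at every p0 shown. The loss of power is serious at low carrier frequencies and small at higher ones.

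**Step 3. Where the attenuation applies.** It concerns variants tied to the syndrome, that is, contrasts of symptomatic participants with other Graves' patients, or the use of the polygenic risk score to predict who is predisposed to cardiac dysfunction. Every participant has Graves' disease whatever the cause of the symptom. A contrast with the general population for variants of Graves' disease itself is therefore not diluted in this way.

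**The case against.** The best defence is that the protocol does more than criterion ## shows. Contact after the questionnaire is limited to people with persistent symptoms. A telephone call before Visit 1 goes through the answers, records and blood tests are reviewed beforehand, and Visit 1 asks about symptoms and other diseases. Staff may exclude anyone they find unsuitable. Appendix 1 and the grading questionnaire are not shown, and either may ask about onset. Broad, symptom-based entry followed by work-up is also a legitimate way to study a condition not yet described, and it matches the Purpose section. The hypothesis speaks of cardiac changes that persist, not of symptoms that must have begun in the hyperthyroid phase.

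Much of this stands, and it rules out three stronger readings.

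- **A reader might infer that any current palpitation or breathlessness is enough.** The contact step does not support that, because it looks for persistence. What remains is that persistence is undefined and is not carried into the criterion.
- **A reader might infer that the Visit 1 information serves no purpose.** It does serve one: history, symptoms and biochemistry are listed among the characteristics to be described. Their use in subgroup analyses may be set out in an analysis plan that is not at hand.
- **A reader might infer a number of misclassified cases** by dividing an assumed background symptom rate by the 38% from the protocol's survey. The documents give no background rate. They also do not show that the survey used the same four symptoms or the same exclusions, so such a figure has no basis.

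The defence does not close the gap. Discretion may remove an evident alternative cause, but nothing requires it, and the example given is language. An onset question in an unseen form would have no effect on entry under ## as written.

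**Conclusion.** The concern holds as a statement about what the criteria permit. Criterion ## lets a self-reported symptom define a case without a link to the hyperthyroid phase, and no listed exclusion removes an evident non-cardiac cause. The case group can therefore mix the hypothesised syndrome with unrelated symptoms. That sits badly with the protocol's claim that its criteria produce a highly selected phenotype.

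The extent of mixing cannot be quantified from the documents. Its direction can be stated under the assumption used above, that cases without the syndrome carry its variants at the control frequency: syndrome-specific odds ratios move towards 1, and the cardiac findings become harder to attribute. The documents do not show that mixing will occur on any particular scale, nor that the broad entry rule is itself a mistake. The correction is worthwhile because it is cheap and because onset that is never recorded cannot be supplied by a later analysis plan.

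**What to change.** 1. Carry the word *persistent* into criterion ## and define it.
2. At Visit 1, record for each reported symptom whether it began before, during or after the hyperthyroid phase.
3. Keep all enrolled participants in the main characterisation.
4. Pre-specify a repeat of the cardiac and genetic analyses restricted to participants whose symptoms began in the hyperthyroid phase and persisted, with haemoglobin within the laboratory reference range and no known lung disease explaining dyspnoea.

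The cost is one question per symptom at an existing visit, a definition, and a few sentences on the restricted analysis. No test is added, since haemoglobin and other diseases are already recorded. The downsides are that onset relies on recall and that the restricted group will be smaller than 80, with less power and the possible loss of some genuine cases. For that reason the restricted group should not replace the full group as the main analysis.

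### Does excluding cardiovascular disease from the cases, but not from the comparators, distort the genetic comparison enough to need a change?

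*Protocol*

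**What the plan says.** In the Protocol, *Exclusion Criteria*, the first criterion for the Graves' patients is "1) Cardiovascular disease", with no further definition. *Inclusion criteria* limits these patients to ages 18 to 55.

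The section on comparison with the Næstved cohort names the comparators. Participants' genotypes are set against variants found in "20,000 of a general population of 70,000 individuals", described as a "control cohort that we already know and have previously genotyped". Findings are then verified in UK Biobank: "The UKBB contains clinical and genetic data on 457 patients" with Graves' disease, and access to its data lets the group "compare our results with similar patients". No cardiovascular limit is stated for either source.

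The trait under study is cardiac. *Hypothesis* holds that Graves' disease "in genetically predisposed individuals will induce cardiac changes", and *Genetic analyses and statistical considerations* uses the polygenic score to "predict who is genetically predisposed to e.g. sinus node and contractile dysfunction". That section also gives the power statement: 80 cases, 200 controls, alpha 0.05 and 80% power for a variant with an odds ratio of 5. It does not say who the 200 controls are.

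**The concern.** A case-control genetic comparison is cleanest when both sides pass the same filters, apart from the trait being compared. Here the filter applied to the cases alone is close to the trait. If people with a high cardiac score are more likely to have diagnosed cardiovascular disease, the exclusion takes high scorers out of the cases and leaves them in the comparators.

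The shift is downwards in the cases. What that does depends on the truth:

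- If cases carry more risk, as the hypothesis expects, the contrast is pulled towards the null.
- If there is no real difference, a small false inverse association appears.
- If a variant is protective, its effect is exaggerated.
- If the score or variant is unrelated to the excluded disease, nothing happens. If the relation is negative, all these directions reverse.

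More controls do not remove the shift. They shrink the standard error around a contrast that stays displaced.

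**Working it through.** **Inputs from the protocol:** 80 cases, 200 controls, alpha 0.05 (taken as two-sided), odds ratio 5, power 80%; 20,000 genotyped in Næstved; 457 Graves' patients in UK Biobank.

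**Assumed, because the protocol gives neither:** prevalence K of cardiovascular disease among otherwise eligible cases, 2-5%; odds ratio g linking the variant (or one SD of score) to that disease, 1.1-1.5.

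**1. The protocol's own target.** A carrier frequency is needed and none is given, so I solved for it. Let p0 and p1 be the carrier frequencies in controls and cases, and p the pooled frequency.

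Power = Φ{[p1 − p0 − 1.96·√(p(1−p)(1/80+1/200))] / √(p1(1−p1)/80 + p0(1−p0)/200)}

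At odds ratio 5, power is 80% when p0 = 2.46% and p1 = 11.19%. Then p = 4.95%, the difference is 0.0873, the critical value is 0.0563 and the denominator is 0.0369. This gives Φ(0.84) = 0.80, which reproduces the stated figure.

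**2. Effect of the exclusion on that target.** With K the prevalence in non-carriers, removing diseased cases multiplies the odds ratio by (1−K_carrier)/(1−K), which simplifies to 1/(1+K(g−1)).

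| K | g | Apparent OR | Power |
|---|---|---|---|
| 2% | 1.1 | 5/1.002 = 4.99 | 79.9% |
| 2% | 1.5 | 5/1.010 = 4.95 | 79.4% |
| 5% | 1.1 | 5/1.005 = 4.98 | 79.7% |
| 5% | 1.5 | 5/1.025 = 4.88 | 78.6% |

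(The last power is 78.7% if K is taken over all cases.) With no true effect, the last row gives 1/1.025 = 0.98.

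*Risk/benefit assessment* says the study works with frequent variants, so 2.46% may be too low. At 5% carriers the worst row moves power from 95.7% to 95.1%; at 10%, from 99.7% to 99.6%.

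**3. A mean-score comparison** (illustrative; the protocol does not state this test). The score is standard normal and the disease follows a logistic model with odds ratio g per SD. The case mean shifts by about −K·ln(g). At K = 5%, g = 1.5 this is −0.05 × 0.405 = −0.0203; numerical integration gives −0.0201. At K = 2%, g = 1.1 it is −0.0019.

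SE = √(1/80 + 1/n). For a true difference set at 80% power, 2.802·SE, the power becomes Φ(0.842 + shift/SE).

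| Controls n | SE | Detectable difference | Power after shift |
|---|---|---|---|
| 200 | 0.1323 | 0.371 SD | 79.6% to 75.5% |
| 457 | 0.1212 | 0.340 SD | 79.6% to 75.0% |
| 20,000 | 0.1120 | 0.314 SD | 79.5% to 74.6% |

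The largest shift is 0.0201/0.1120 = 0.18 SE. With no true difference it gives 5.4% rejections in place of 5% (n = 20,000).

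**4. Screening the controls.** Næstved is described as "the Næstved cohort which has been followed over 20 years". Suppose controls were dropped for disease at any time in that period. Assume 20% affected, against 5% among cases at entry, and g = 1.1-1.5. The false difference is then about (0.20 − 0.05)·ln(g); exactly, +0.014 to +0.059 SD. The false-positive rate with 20,000 controls is 5.2-8.2%. At g = 1.5 the mis-dated filter makes an error about three times the one it was meant to remove (0.059 against 0.020 SD).

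**The case for a change.** The best argument for acting is that the imbalance is stated in the protocol itself: the case restriction and the comparison populations are both fixed there. Its size is bounded only by assumption. At 10% prevalence and an odds ratio of 1.5 per SD, the shift is −0.040 SD and power in the illustrative score test falls to 71% with 200 controls and 69% with 20,000. At 20% and an odds ratio of 2 it is −0.129 SD, with 45% and 38%; the odds ratio of 5 becomes 4.17. A filter on the controls costs almost no precision: the detectable difference goes from 0.314 to 0.319 SD if 2,000 of 20,000 remain (an assumed number).

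The asymmetry and the arithmetic stand. The large losses need cardiovascular disease to be common among patients aged 18 to 55 and strongly predicted by the score. Nothing in the protocol supports either.

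Nor does the protocol rule out screened controls. The 200 counted for power are not described, *Genetic analyses* refers separately to control groups, and the clinical data in UK Biobank would allow selection of comparable people. Those details are commonly left to the statistical analysis plan.

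Excluding known cardiovascular disease also has a purpose. It removes patients whose symptoms may have another explanation and who need not belong to the proposed syndrome. Setting that phenotype against the general population answers a legitimate question; setting it against disease-free controls answers a slightly different one.

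**Conclusion.** The imbalance is real, but it leaves the planned comparison sound. Under 2-5% prevalence and a disease odds ratio of 1.1-1.5, it takes at most about 2.5% off the target odds ratio (5 to 4.88) and about 1.4 percentage points off the stated power. In a score comparison that the protocol does not specify, the worst corner of the same range costs 5.4 points (80% to 74.6%). The direction is downwards in the cases, and so towards the null only if cases truly carry more risk. These sizes rest on the assumed prevalence and association, and would grow if both were much larger.

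Screened or unscreened controls is a fair trade-off. A filter helps only if diagnoses are dated and applied at an age comparable with the cases. For Næstved the protocol mentions genotypes and follow-up, not dated diagnoses. Without those dates, the sensible course is the unrestricted comparison already planned. Where dates exist, analysts can add a restricted comparison as a sensitivity analysis without any change to the protocol.
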